## **DATA SAFETY MONITORING**

The National Institute on Aging-approved data safety monitoring plan and appointment of the safety officer is provided in the Appendix.

## **DATA COLLECTION AND QUALITY ASSUARANCE**

The only people who will know that these patients are research participants are members of the research team. No information about them, or provided by them during the research, will be disclosed to others without their written permission, except if it is necessary to protect their rights or welfare (for example, in case of injury or emergency care), or if it is required by law. When the results of the research are published or discussed in conferences, no information will be included that would reveal the identity of these patients. All data will be kept in locked files, and subjects will be identified by codes when the data gathered in this procedure is presented or published. Authorized representatives of the National Institutes of Health may need to review records of individual participants. As a result, they may see their name; but they are bound by rules of confidentiality not to reveal the patients' identity to others.

### **Privacy**

The subjects will be interviewed in the privacy of an exam room and their records will be protected by a secure medical records area and a password-protected electronic database monitored by the Pennington Research Computing group. Subjects will be asked to sign a written consent after reading it, having it reviewed with them by the study staff and having all their questions answered. The consent conversation will be conducted in the privacy of an exam room and the subject will be allowed to take the consent home to discuss their decision with their family or counselor, if desired. Study procedures will be conducted by trained staff in accordance with PBRC outpatient clinic standards of practice and with subjects' informed consent. Confidential subject information including medical records and test results will be available only to persons authorized by the Pennington. Information collected from subjects will be the minimum amount of data necessary to accomplish the research purposes.

### **Data and Specimen Management**

Study participants will be assigned unique subject identification (ID) numbers. Study subject ID numbers will be used on all data collection instruments, to include questionnaires, data collection forms, and computer records. The forms used for data collection and questionnaires such as the medical history questionnaire will be the standard forms used in PBRC studies. A master list linking the participants' names and ID numbers will be kept in a password-protected computer file with access restricted to the PI and co-PI's. Data collection forms will be kept secure, or password-protected if computerized, and under the control of the PI, co-PIs, and medical investigator. Only personnel assigned to the research study by the PI will have access to the data. Hard-copy data records will be stored for a minimum of 3 years.

The PBRC has a fully integrated, campus-wide, automated data management system. All data are entered into a central database using existing methodology that has been fully validated and undergoes continuous quality assurance by the PBRC Research Computing Core. All data are backed up daily, and the Research Computing Core at the PBRC oversees all data management. The research team has extensive experience using the procedures and methods required to conduct this study. Standard operating procedures in place throughout the units at Pennington Biomedical will be utilized for repeatable, valid data collection and quality.

In accordance the standards of practice followed by the Clinical Chemistry core, blood samples will be stored frozen at PBRC until analysis can be completed. Fecal samples will be shipped to Scioto Biosciences, Indianapolis, IN for analysis. Packaging and shipping of biological samples will be overseen by the PI, shipped by the laboratory and will be completed in accordance with

International Air Transport Association regulations to ensure that viable biological samples reach their intended destination.

### **WITHDRAWAL OF SUBJECTS**

We will attempt to retain program participants once randomized for study completion through the end of study visit. It is our desire to analyze results on all participants who were enrolled in the study. In accordance with the declaration of Helsinki/Tokyo/Venice/Hong Kong, participants have the right to withdraw from the program at any time for any reason. The investigator also has the right to withdraw participants from the program treatments in the event of inter-current illness, adverse experience, treatment failure, protocol violation, or other reasons. Should a participant decide to withdraw from treatment, all efforts will be made to complete and report follow-up observations as thoroughly as possible.

### **PAYMENT FOR PARTICIPATION**

At the completion of all study visits and procedures, participants will be paid \$125 for the time spent in the clinic. If subjects' participation in the study ends early, they will receive \$25 for completion of each visit. This compensation is in line with all the other studies conducted at the Pennington Biomedical Research Center.

### **EMERGENCY CARE AND COMPENSATION FOR RESEARCH-RELATED INJURY**

No form of compensation for medical treatment is available from the Pennington Biomedical Research Center. In the event of injury or medical illness resulting from the research procedures the research volunteer (from any group) will be referred to their physician/surgeon or a treatment facility. The Pennington Biomedical Research Center is a research facility and provides medical treatment only as part of research protocols. Should a volunteer require medical treatments, community physicians and hospitals must provide them to him/her.

### **SHARING OF RESULTS WITH SUBJECTS**

The screening lab will be shared with the subjects on their first testing visit. At the end of the study, a manuscript will be prepared for submission to a peer-reviewed journal. A summary of the results will be posted on ClinicalTrials.gov which subjects may access. Since subjects are elderly, a written summary will be provided.

### **RESOURCES AVAILABLE**

The outpatient research units are well equipped and staffed to carry out the requirements of this study and appropriate standards of practice are in place to ensure appropriate research procedures.

### **ECONOMIC BURDEN TO SUBJECTS**

There are no costs for which the subjects will be responsible.

### **CONSENT PROCESS**

Written informed consent will be obtained in the outpatient research clinic by the coordinators and one of the physicians will be available to answer questions if needed. A waiting period will be allowed, if desired by the participant. The coordinators and investigators will be available for questions throughout the study.

### Lifestyle intervention to reduce apathy in the elderly

**Brief Description of Intervention:** To determine an acceptable dose of dietary fiber from soy, a dose escalation trial in eight older subjects with obesity will be conducted. The tolerability to soft foods containing approximately 4 g, 8 g, and 12 g/day of dietary fiber (depending on the nutrition analysis of the soy flour) from 10g, 20g, and 30g of soy flour for one week at each dose will be assessed, and the maximum tolerated dose will be determined.

#### **Brief Description of Project Design**

- Eight subjects will consume soft foods containing soy along with their regular diet for one week.
- Compliance will be assessed from an interview with the subject and an evaluation of used and unused containers returned by subjects.
- Subjects will provide a stool sample for measurement of short chain fatty acids as an objective biomarker of compliance.
- Subjects will complete a tolerability questionnaire at the end of each week. If a dose is tolerated, subjects will receive the next escalated dose for one week.

#### **Stage of Behavioral Intervention Development** Stage I

**NIH Phase III Clinical Trial?** No.

**Multiple Site Trial?** No.

#### **List of Specific Aims**

- Determine the maximum tolerated dose of dietary fiber from soy in elderly subjects with obesity and measure fecal short chain fatty acids (SCFA) as a biomarker of compliance.

## 1.0 PARTICPANTS SAFETY

### 1.1 Potential Risks and Benefits for Participants

The study involves the following procedures which may pose a potential risk:

- **Blood Draws.** There is the possibility of discomfort, pain, and bruising at the vein on the arm where the needle is inserted. There may also be a small risk of bleeding and a very small risk of infection at the site of the blood draw. Sterile technique and trained personnel minimize these risks.
- **Safety Assessments.** Complete blood count (CBC), and chemistry 15 panel (glucose, creatinine, potassium, uric acid, albumin, calcium, magnesium, creatine phosphokinase, alanine aminotransferase, alkaline phosphatase, iron, cholesterol [total, high density lipoprotein, low density lipoprotein], and triglycerides) reports will be used to screen for eligibility prior to enrollment and will be used as a safety assessment following completion of each dose of dietary fiber during the study. The medical investigator will review the reports, and clinically significant changes in laboratory values will be investigated, and the subject will be referred for treatment, as appropriate.
- **Whole soy pods.** The soy being tested in the study is a food. The soybean will be grown at the Louisiana State University (LSU) Agricultural Center and milled to a flour at the United States Department of Agriculture (USDA, New Orleans, LA.) Food Processing and Sensory Quality Research Unit, where scientists work with foods for research purposes. This research examines an approach that mimics soybean consumption from parts of the world where its efficacy and health benefits are known. We expect that subjects will experience GI symptoms from increased dietary fiber intake, but from the applicant's practice as a registered dietitian and evidence in the literature we know that these symptoms resolve. In the general population, supplementation with dietary fibers such as inulin and guar gum is well-tolerated at 15 g/day. Therefore, we expect that supplementation of the usual diet with 4 g, 8 g, and 12 g dietary fiber from soy will be tolerated by the elderly.
- **Study Foods.** There is ordinarily no risk associated with the foods provided by the Pennington Metabolic kitchen. Additionally, subjects will be asked to inform staff about any food allergies or intolerances. A dietary questionnaire is routinely administered at the screening visit when the study involves a meal service. Research dietitians are responsible for managing the dietary component of specific study protocols. A continuous quality assurance program is followed to check food item weights, recipe procedures, packed meal and tray assembly, and food temperatures. Documentation is maintained for each study. All Metabolic Kitchen staff members receive training in food sanitation and in research diet preparation.
- **Anthropometric Measurements and Vital Signs.** The PBRC outpatient clinic staff are trained to perform these procedures in accordance with PBRC standards of practice.
- **Fecal Samples.** The clinical chemistry core staff will collect the fecal samples in accordance with standard operating practices.

In addition to the potential risks listed above, participants may experience a previously unknown risk or side effect.

## Potential Benefits

Constipation is a common problem in the elderly. With the increase in dietary fiber, participants may experience benefits in their bowel movements, and as a result, in their general well-being.

## 1.2 Adverse Event and Serious Adverse Event Collection and Reporting

### Unanticipated Problem

An unanticipated problem is any incident, experience, or outcome that meets all of the following criteria: (1) unexpected, in terms of nature, severity, or frequency, given (a) the research procedures that are described in the protocol-related documents, such as the IRB-approved research protocol and informed consent document; and (b) the characteristics of the study population; (2) related or possibly related to participation in the research (possibly related means there is a reasonable possibility that the incident, experience, or outcome may have been caused by the procedures involved in the research); (3) suggests that the research places participants or others at a greater risk of harm (including physical, psychological, economic, or social harm) than was previously known or recognized. Unanticipated problems include other incidents, experiences, and outcomes that are not adverse events.

### Adverse Events

An Adverse Event (AE) is defined as any untoward medical occurrence in a patient or clinical investigation subject, temporally associated with the use of a medicinal product, whether or not considered related to the medicinal product. We define AE as any unfavorable and unintended sign (including a clinically significant abnormal laboratory finding), symptom, or disease (new or exacerbated) temporally associated with the use of the study food.

We will define a serious adverse event (SAE) as any untoward medical occurrence that results in death, is life threatening, requires inpatient hospitalization or prolongation of existing hospitalization, results in persistent or significant disability/incapacity or in a congenital anomaly.

Safety will be assessed by recording all adverse events. The study team will inquire regarding adverse events while minimizing the chance for bias when detecting AEs/SAEs. The study team will employ open-ended and non-leading verbal questioning of the subject as the preferred method to inquire about AE occurrence. For examples, appropriate questions include: "How are you feeling?", "Have you had any (other) medical problems since your last visit/contact?", or "Have you taken any new medicines since your last visit/contact?" It is the responsibility of the investigator to attempt to establish a diagnosis of the event based on signs, symptoms, and/or other clinical information. In such cases, the diagnosis will be documented as the AE/SAE and not the individual signs/symptoms.

**Assessment of Intensity.** An assessment of intensity for each AE and SAE reported during the study will be provided by the investigator and the investigator will assign it to one of the following categories:

Mild: An event that is easily tolerated by the subject, causing minimal discomfort and not interfering with everyday activities.

Moderate: An event that is sufficiently discomforting to interfere with normal everyday activities.

Severe: An event that prevents normal everyday activities.

An AE that is assessed as severe will not be confused with an SAE and both AEs and SAEs can be assessed as severe. Severe Adverse Event is a category utilized for rating the intensity of an event.

**Assessment of Causality.** The investigator is obligated to assess the relationship between study treatment and the occurrence of each AE/SAE. A "reasonable possibility" is meant to convey that there are facts/evidence or arguments to suggest a causal relationship, rather than that a relationship cannot be ruled out. The investigator will use clinical judgment to determine the relationship. Alternative causes, such as concomitant therapy, other risk factors, and the temporal relationship of the event to the study treatment will be considered and investigated.

***Events meeting the definition of an AE:***

- Any abnormal laboratory test results (clinical chemistry) or other safety assessments (e.g., vital signs measurements), including those that worsen from baseline, and felt to be clinically significant in the medical and scientific judgment of the investigator.
- Exacerbation of a chronic or intermittent pre-existing condition including either an increase in frequency and/or intensity of the condition.
- New conditions detected or diagnosed after study treatment administration even though it may have been present prior to the start of the study.
- Signs, symptoms, or the clinical sequelae of a suspected interaction.
- Signs, symptoms, or the clinical sequelae of a suspected overdose of either study treatment or a concomitant medication (overdose per se will not be reported as an AE/SAE).

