## RESEARCH DESIGN AND METHODS

To determine an acceptable dose of DF, we will conduct a dose escalation trial in eight elderly subjects with obesity and test the tolerability to soft foods containing 4 g, 8 g, and 12 g of DF/day from soy for one week at each dose. The soy contains approximately 39% DF. Therefore, subjects will consume soft foods containing 10 g, 20 g, and 30 g of soy/day to provide the required DF doses and the phytonutrients in soy. This clinical trial is patterned according to the National Cancer Institute's (NCI's) recommendation for dose escalation to determine toxicity to a drug. We are testing a food, and we know that relatively large doses of DF are tolerated if daily intake is divided into small portions throughout the day. However, we will evaluate tolerability to DF from soy, and measure fecal SCFA as a biomarker of compliance with the intervention. The maximum recommended starting dose (MRSD) for DF may be estimated at 4 g which added to average DF intake in the US of approximately 17g is not in excess of the recommended adequate intake of 25 - 38 g/day. The dose escalation scheme recommended for first-in-human trials is rapid dose escalation initially (MRSD x 2) until the estimated desirable dose (8 g) is reached and then at a more cautious escalation (e.g. MRSD x 1.5). Subjects will consume soft foods containing 4 g/day of DF from soy for one week, then proceed to 8 g/day for one week, followed by 12 g/day for one week, incorporated into their usual diet.

Adverse events will be recorded as they occur and collated for each week. Fecal SCFA and gastrointestinal (GI) symptoms will be evaluated at the end of each week (Figure 2).

[figure not shown]

Figure 2. Study schema

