**Table 1. Schedule of Assessments for Dose Response Study**

Procedure	Screening 1	Baseline	Visit 1	Visit 2	Visit 3
PBRC Outpatient Unit					
Infomed Consent	X				
Height	X				
Weight, and Vital Signs	X	X	X	X	X
Chemistry 15 Panel/CBC	X				X*
Medical History Questionnaire	X				
MMSE and GDS-15	X				
Adverse Events**			X	X	X
Medications	X	X	X	X	X
Tolerability Questionnaire**		X	X	X	X
Food Dispensation		X	X	X	
Nutrition Counseling**		X	X	X	
Compliance with Study Foods			X	X	X
Fecal Sample (SCFA)***		X	X	X	X
Fecal Sample (Archives)	X	X	X	X	

\* Or at a prior visit if the dose is not tolerated

\*\* By phone call on day prior to the study visit.

\*\*\*Measured at Scioto Biosciences

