### **Visit 1 (Week 1, 1 hour)**

Assessment of adverse events, completion of the tolerability questionnaire, and nutrition counseling will be completed by phone on the day prior to the visit to avoid unnecessary food preparations in the event that the participant does not tolerate the dose. Subjects will report to the clinic for the visit and the following tests and measurements will be performed:

- Collection of fecal sample.
- Measurement of weight and vital signs.
- Recording of changes in medications.
- Dispensation of study foods.
- Assessment of compliance by metabolic kitchen staff.

- Dispensation of stool collection kit.

A blood draw for CBC/Chemistry panel will be performed if participants are not being advanced to the next dose. Participants will be advised to report after a ten hour fast.

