## **STUDY PROCEDURES**

**Whole soy pods (soy).** The plants will be grown under carefully monitored conditions at the LSU Agricultural Center and harvested at reproductive stage six or when the green pods contain soybeans that fill the pods. The whole pods will be processed at the United States Department of Agriculture (USDA, New Orleans, LA), Food Processing and Sensory Quality Research Unit, where scientists work with foods for research purposes. Slicing the pods into thin cross-sections injures plant cells and activates the synthesis of an anti-microbial compound (glyceollin) synthesized by the plant *de novo* in response to stress. Glyceollins have been shown to improve insulin sensitivity and cognition. The sliced pods will be lyophilized and milled. Nutrient analysis, will be performed at Eurofins Food Chemistry Testing (Madison, WI) using methods of analysis of the Association of Official Analytical Chemists.

**Food Development.** The soy will be incorporated in foods and prepared by the PBRC metabolic kitchen. The PBRC metabolic kitchen is staffed with research dietitians who have a primary responsibility to develop foods for research purposes, plan diets, and execute their delivery. In addition, the applicant is a registered dietitian with experience in food development across cuisines and cultures.

**Nutrition Counseling.** Subjects will be counseled by the study dietitian who will interview the subject in order to assess the subject's current intake. Based on this information, subjects will be counseled on incorporating the test foods in their diet. We expect that subjects will experience GI symptoms from increased DF intake, but from the applicant's practice as a

registered dietitian and evidence in the literature we know that these symptoms resolve. To enhance compliance with the protocol, subjects will receive counseling on managing GI symptoms.

**Food Tolerability.** Subjects will complete a version of the GI symptoms questionnaire designed as a validated assessment for dyspepsia, and modified to make it specific by only including the symptoms that may be experienced with high DF intake. The scale is ranked as none, mild, moderate, and severe for each of four GI symptoms (bloating, abdominal rumbling, flatulence, and abdominal pain). Additionally, subjects will report their stool frequency ranging from 0 to 9+, and stool consistency based on the Bristol Stool scale.

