***Events that do not meet the definition of an AE:***

- Any clinically significant abnormal laboratory findings or other abnormal safety assessments that are associated with the underlying disease, unless judged by the investigator to be more severe than expected for the subject's condition.
- Medical or surgical procedure (e.g., endoscopy, appendectomy); the condition that leads to the procedure is an AE
- Situations where an untoward medical occurrence did not occur (social and/or convenience admission to a hospital).
- Anticipated day-to-day fluctuations of pre-existing disease(s) or condition(s) present or detected at the start of the study that do not worsen.

AEs will be reported per IRB policies, and to the NIA on an annual basis. The reporting of AEs will follow the standards of practice as outlined by the Pennington Biomedical Research Center (PBRC) IRB in the 'Unanticipated problems Involving risks to subjects or others' policy. Once the investigator determines that an event meets the definition of an AE that must be reported, the investigator will not wait to receive additional information before notifying the responsible parties of the event and completing the appropriate forms. An assessment of causality at the time of the initial report will be provided. Email transmission of the AE data collection tool will be the preferred method to transmit this information followed by notification by telephone and/or

fax. A copy of the AE report will also be sent to the institution officials. New or updated information will be recorded in the originally completed data collection tool.

We are testing tolerability to a dietary fiber at supplementation levels known to be tolerated. In some instances, increased intake of dietary fiber may result in gastrointestinal symptoms which resolve over time. Nevertheless, should an SAE occur, a summary will be reported to NIA Program Officer and to the Safety Officer quarterly, in accordance with NIA policies. When SAEs occur that are unexpected (i.e., have not been previously reported for the study's intervention) and that are related to the intervention, they will be reported to NIA Program Officer and to the Safety Officer within 48 hours of study's knowledge of the SAE. All deaths will be reported within 24 hours of study's knowledge of death. The report of death will be submitted to NIA Program Officer and to the Safety Officer.

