## 2.0 INTERIM ANALYSIS

The primary objective of the study is to determine the maximum tolerated dose of dietary fiber. Dose safety will be investigated by compiling by treatment (e.g. 4 g dose, 8 g dose, 12 g dose) a list of adverse events such as frequency of headaches, nausea, vomiting. For GI symptoms the scale is ranked as none (no symptoms), mild, moderate, and severe for each of four GI symptoms and the assessment of intensity is provided in the section on adverse events.

Moderate and severe ratings will be considered intolerance to the dose. Stool frequency of one to three/day, or three times/per week is considered regular. Therefore, stool frequency of less than one and more than nine over a 72-hour period will be a consideration for determining intolerance. Stool consistency of Type three to five on the Bristol Stool Scale is considered normal. Any other rating will be considered in the determination of intolerance. To be considered intolerance, subjects must rate stool frequency and consistency as being of moderate to severe intensity. If a dose is tolerated, subjects will receive the next escalated dose for one week.

**Stopping Rules.** The study foods will be stopped, and further dosing will be halted until un-blinded safety information can be reviewed in the event that:

- A death occurs.
- Two or more subjects experience the same SAE following administration of study product.
- Based on AEs, laboratory findings, or clinical findings the Investigator determines that review of pertinent safety information is required.

Dosing may only resume if, after review of safety information, both the Investigator and IRB agree that it is safe to proceed.

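### Headache, nausea and vomiting are compiled by soy dose, but no inquiry about them is scheduled before soy starts

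*Combined protocol and SAP*

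**What the plan says.** **Use of the list.** Sample Size and Analysis, and section 2.0 of the data safety monitoring plan, investigate dose safety by compiling, for each dose, "a list of adverse events such as frequency of headaches, nausea, vomiting". Section 3.3 of that plan confirms that every subject receives the study product.

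**Timing of the inquiry.** In Table 1 the row "Adverse Events" is marked at Visits 1, 2 and 3 only. The item lists for the Screening and Baseline visits contain no adverse event or current-symptom item. The first scheduled inquiry is the call before Visit 1, at the end of the 4 g week: "Assessment of adverse events, completion of the tolerability questionnaire, and nutrition counseling will be completed by phone on the day prior to the visit". Research Design and Methods adds: "Adverse events will be recorded as they occur and collated for each week".

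**What is rated before soy.** The tolerability questionnaire is completed at Baseline. It grades "each of four GI symptoms (bloating, abdominal rumbling, flatulence, and abdominal pain") and also takes stool frequency and consistency. Headache, nausea and vomiting are not on it. A self-reported medical history is taken at Screening, and medications are recorded at Screening and Baseline.

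**What counts as an adverse event (section 1.2).** The general definition covers a "symptom, or disease (new or exacerbated) temporally associated with the use of the study food". The list of qualifying events includes "New conditions detected or diagnosed after study treatment administration even though it may have been present prior to the start of the study" and any increase in the frequency or intensity of a pre-existing condition. The list of non-qualifying events includes "Anticipated day-to-day fluctuations of pre-existing disease(s) or condition(s) present or detected at the start of the study that do not worsen". The investigator assesses causality for each event.

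**The concern.** A frequency tabulated by dose will be read as a statement about the doses. Headache and nausea also occur in people who eat no soy, so the reader needs to know how often these subjects had them beforehand. There is no control group, and a soy-free period is the only thing that could show the level at 0 g.

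The plan takes pre-soy values for gastrointestinal symptoms, fecal short chain fatty acids, weight, vital signs and laboratory tests. It schedules none for the complaints that it names as examples for the adverse event list. Whether such a complaint is new, worsened or unchanged then depends on what the subject happened to mention in the medical history.

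At stake is the reading of a descriptive safety table. That table may inform the discretionary stopping rule in section 2.0, which rests on the investigator's judgement of adverse events, and the toxicity information sent to the Safety Officer under section 3.3.

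**Working it through.** The plan gives no figure on this point, so there is nothing to reproduce. The check compares what the definitions need with what is collected, and then gives a scale.

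**1. What the definitions need.** Deciding whether an event is new requires knowing whether it was present before soy. Deciding whether it is exacerbated requires its earlier frequency or intensity. Excluding it as pre-existing and unworsened requires both.

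**2. What is collected before soy.**

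| Complaint | Scheduled pre-soy record |
|---|---|
| Bloating, rumbling, flatulence, abdominal pain | Graded at Baseline |
| Stool frequency and consistency | Recorded at Baseline |
| Headache, nausea, vomiting | None specific; only what emerges from the medical history or medication record |

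The medical history form is a standard form of the centre (Data and Specimen Management) and its items are not shown. The protocol does not specify that it counts recent headaches or nausea.

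**3. Scale.** The inputs are:

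- Number of subjects n: 10 (Study Subjects; Sample Size and Analysis) or 8 (Research Design and Methods). The documents give both, so both are shown.
- b, the proportion of subjects with such a complaint in an ordinary week. The documents give no value; 10%, 20% and 30% are assumed.
- Subjects are taken as independent, and soy as having no effect.

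Expected number of subjects with a background complaint in one dose week = n × b. Chance of at least one = 1 − (1 − b)^n.

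| b | n = 10: expected | n = 10: at least one | n = 8: expected | n = 8: at least one |
|---|---|---|---|---|
| 10% | 1.0 | 1 − 0.9^10 = 65% | 0.8 | 1 − 0.9^8 = 57% |
| 20% | 2.0 | 1 − 0.8^10 = 89% | 1.6 | 1 − 0.8^8 = 83% |
| 30% | 3.0 | 1 − 0.7^10 = 97% | 2.4 | 1 − 0.7^8 = 94% |

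At b = 5% the chances are 40% (n = 10) and 34% (n = 8).

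For each assumed rate these are upper bounds. Complaints already known and not worsened are excluded under section 1.2, and subjects who do not tolerate a dose do not contribute to later weeks.

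**4. Effect on the table.** Suppose 2 of 10 subjects have a weekly background complaint that goes unmentioned before soy. With events collated each week, the list reads 2, 2, 2 at 4, 8 and 12 g. A soy effect in 2 of 10 subjects at every dose, with no background, gives the same list. A 0 g entry would be 2 in the first case and 0 in the second.

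**The case against.** The case on the other side is substantial, and most of it limits the point.

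- **Known conditions are already excluded.** A reader might infer from the rule on newly detected conditions that everything present before the study becomes an adverse event. It does not: the general definition and the list of non-qualifying events remove known conditions that do not worsen. The gap is confined to complaints whose earlier state was not recorded.
- **Nothing is attributed to soy by definition.** The rule decides what is recorded. Section 1.2 separately requires a causality assessment that weighs alternative causes. That stands, although the by-dose list is not restricted to events judged related, and the assessor also lacks the earlier frequency.
- **The 4 g column is not singled out.** One might expect background complaints to pile up at 4 g and give a false decline such as 2, 0, 0. That needs a rule listing each complaint only when first detected. The documents contain no such rule; weekly collation points the other way. All three columns share the problem.
- **The same subjects take each dose, so weeks can be compared.** Such comparisons can show a change between doses but not the level common to all of them. Dose also rises with week in fixed order.
- **The list is descriptive.** No test or numerical threshold is attached to it, and the maximum tolerated dose rule uses gastrointestinal ratings and stool measures. This stands and keeps the consequence small.
- **Counting newly detected conditions is a deliberately conservative safety rule, and an adverse event is tied to use of the study food.** Both stand. The remedy should neither change the definition nor call pre-soy complaints adverse events.

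**Conclusion.** The point holds in a limited form. The plan tabulates headache, nausea and vomiting by dose without any scheduled inquiry about them before the first soy food. Its own tests of new, exacerbated or unworsened therefore lack a systematically recorded prior state for these complaints, and with no control group the list cannot separate background from soy effects in any dose week.

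If 10% to 30% of subjects have such a complaint in an ordinary week, the chance of at least one background entry in a given dose week is at most 65% to 97% with 10 subjects, or 57% to 94% with 8. The rates are assumed, not taken from the documents. The result also rests on independent subjects and on the unseen medical history form not already capturing recent complaints.

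The documents do not support reading this as a bias in the maximum tolerated dose, a distortion peculiar to 4 g, or a fault in the adverse event definition. It is a cheap improvement to a stated safety analysis.

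**What to change.** 1. At the Baseline contact where the tolerability questionnaire is already completed, before any soy is eaten, put the open questions of section 1.2 to the subject with reference to the previous seven days. Add this item to the Baseline visit list and to Table 1.
2. Record the answers as pre-soy symptoms, not as adverse events.
3. Add a 0 g column to the by-dose list in Sample Size and Analysis and in section 2.0 of the data safety monitoring plan. In the dose columns, flag complaints that the subject already had before soy.
4. Leave the reporting definition in section 1.2 unchanged.

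The cost is a few minutes per subject at a contact that already takes place, one more schedule entry and one more table column. The drawback is reliance on seven-day recall. The change must be in place before dosing, because a prospective pre-soy record cannot be obtained once soy has started.
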